Appendix 1 SCHEDULE OF ASSESSMENTS
Original Wording from Clinical Protocol Version 1,
Date 16 Jun 15
(Deleted wording is struck through and in bold)

Blinded Phase

Visit Number	1	2	3	4	5	6	7	8	9	10	11 (Tel.)	Safety Calls*
Informed consent/assent	X											
Eligibility Criteria	X	X										
Randomization		X										
Demographics	X											
Medical history	X											
Vital signs	X	X	X	X	X	X		X	X	X		
Postural BP	X	X										
Physical examination (including height and body weight)	X	X	X	X	X	X		X	X	X		
ECG	X	X	X	X	X	X		X	X	X		
Clinical laboratory blood sampling	X	X	X	X	X	X		X	X	X		
Clinical laboratory urine sampling (dipstick urinalysis)	X	X	X	X	X	X		X	X	X		
Urine THC screen	X	X							X			
Pregnancy test (if appropriate)	X	X							X			
Pharmacokinetic blood sampling		X							X			
AED concentration		X		X		X		X	X			
AEs	X	X	X	X	X	X	X	X	X	X	X	X
Concomitant medications	X	X	X	X	X	X	X	X	X	X	X	X
Inpatient epilepsy-related hospitalizations		X	X	X	X	X	X	X	X	X	X	X
Suicidality / C-SSRS/Children's C-SSRS	X	X	X	X	X	X		X	X	X		
Vineland-II		X	X	X	X	X		X	X			
SGIC/CGIC			X	X	X	X		X	X			
PGIC			X	X	X	X		X	X			
SGIC-SD/CGIC-SD									X			
QOLCE/QOLIE-31-P		X							X			
Wechsler Tests		X							X			
CBCL/ABCL		X							X			
SCQ		X							X			
Tanner Staging (where appropriate) and IGF-1 testing		X							X			
Menstruation question (where appropriate)		X							X			
Patient diary review (seizures, AE information, concomitant AEDs, rescue medication, IMP dosing)		X	X	X	X	X		X	X	X		
IVRS and diary training	X											
IMP dispensing		X	X	X	X	X		X	X			
Collection of IMP			X	X	X	X		X	X	X		
IMP compliance review			X	X	X	X		X	X	X		
Study Medication Use and Behavior Survey									X			

Revised Wording from Clinical Protocol Amendment 1
(Clinical Protocol Version 2, Date 21 Oct 15)
(Revised wording is underscored and in bold)

Blinded Phase

Visit Number	1	2	3	4	5	6	7	8	9	10	11	12 (Tel.)	Safety Calls*
Informed consent/assent	X												
Eligibility Criteria	X	X	X										
Randomization			X										
Demographics	X												
Medical history	X												
Vital signs	X		X	X	X	X	X		X	X	X		
Postural BP	X		X										
Physical examination (including height and body weight)	X		X	X	X	X	X		X	X	X		
ECG	X		X	X	X	X	X		X	X	X		
Clinical laboratory blood sampling	X		X	X	X	X	X		X	X	X		
Clinical laboratory urine sampling (dipstick urinalysis)	X		X	X	X	X	X		X	X	X		
Urine THC screen	X		X							X			
Pregnancy test (if appropriate)	X		X							X			
Pharmacokinetic blood sampling			X							X			
AED concentration			X		X		X		X	X			
AEs	X	X	X	X	X	X	X	X	X	X	X	X	X
Concomitant medications	X	X	X	X	X	X	X	X	X	X	X	X	X
Inpatient epilepsy-related hospitalizations		X	X	X	X	X	X	X	X	X	X	X	X
Suicidality / C-SSRS/Children's C-SSRS	X		X	X	X	X	X		X	X	X		
Vineland-II			X	X	X	X	X		X	X			
SGIC/CGIC			X	X	X	X	X			X			
PGIC			X	X	X	X	X			X			
SGIC-SD/CGIC-SD			X							X			
QOLCE/QOLIE-31-P			X							X			
Wechsler Tests			X							X			
CBCL/ABCL			X							X			
SCQ			X							X			
Tanner Staging (where appropriate) and IGF-1 testing			X							X			
Menstruation question (where appropriate)			X							X			
Patient diary review (seizures, AE information, concomitant AEDs, rescue medication, IMP dosing)			X	X	X	X	X		X	X	X		
IVRS and diary training		X											
IMP dispensing			X	X	X	X	X		X	X			
Collection of IMP				X	X	X	X		X	X	X		
IMP compliance review				X	X	X	X		X	X	X		
Study Medication Use and Behavior Survey										X			

A double-blind, randomized, placebo-controlled study to investigate the efficacy and safety of cannabidiol (GWP42003-P, CBD) as add-on therapy in patients with tuberous sclerosis complex who experience inadequately-controlled seizures

Study Code: GWEP1521

EudraCT Number: 2015-002154-12

CLINICAL PROTOCOL ANNEX 1
(US ONLY)

This annex outlines the assessments and procedures for years 2–4 of the open-label extension. This annex will be implemented at US sites only.

GW Research Ltd
[name]
United Kingdom

Tel: PPD [REDACTED]
Fax: PPD [REDACTED]

Confidentiality Statement

This document contains confidential information of GW Research Ltd (GW) that must not be disclosed to anyone other than the recipient study staff and members of the institutional review board or independent ethics committee. This information cannot be used for any purpose other than the evaluation or conduct of the clinical investigation without the prior written consent of GW.

Investigator Agreement

APPENDIX 1 SCHEDULE OF ASSESSMENTS	15

List of Abbreviations

ABCL	Adult Behavior Checklist
AE	Adverse event
AED	Antiepileptic drug
CBCL	Child Behavior Checklist
CBD	Cannabidiol
CGIC	Caregiver Global Impression of Change
CGIC-SD	Caregiver Global Impression of Change in Seizure Duration
C-SSRS	Columbia-Suicide Severity Rating Scale
ECG	12-lead electrocardiogram
EU	European Union
FDA	US Food and Drug Administration
GCP	Good clinical practice
GW	GW Research Ltd
IGF-1	Insulin-like growth factor-1
IMP	Investigational medicinal product
IVRS	Interactive voice response system
OLE	Open-label extension
PGIC	Physician Global Impression of Change
QOLCE	Quality of Life in Childhood Epilepsy
QOLIE-31-P	Quality of Life in Epilepsy
SCQ	Social Communication Questionnaire
SGIC	Subject Global Impression of Change
SGIC-SD	Subject Global Impression of Change in Seizure Duration
TSC	Tuberous sclerosis complex

(continued)

US United States
Vineland-II Vineland Adaptive Behavior Scales, Second Edition

Definition of Terms

Term	Definition
End of trial	Last patient last visit or last contact, whichever occurs last.
Enrolled patient	Any patient who has provided written informed consent/assent to take part in the trial.
Investigational medicinal product	Term used to describe both investigational active product and reference therapy (placebo).
Investigator	Trial principal investigator or a formally delegated study physician.

1 RATIONALE

Trial GWEP1521 consists of a randomized, parallel-group, 16-week double-blind-phase comparing 2 doses of GWP42003-P with placebo, followed by a 1-year open-label extension (OLE) phase. To ensure continued access to GWP42003-P prior to approval, the OLE phase will be extended to a total of 4 years in duration in the United States (US). Patients will complete the OLE phase when GWP42003-P is approved in tuberous sclerosis complex (TSC) and is commercially available to the patient, or after a maximum of 4 years of OLE treatment, whichever occurs first.

[figure not shown]
2 SUMMARY OF THE ANNEX

Patients will complete the first year of the OLE at Visit B10 and enter a second year of OLE treatment. Patients completing a second year of OLE treatment will enter a third year of OLE treatment. Patients who complete OLE year 3 may enter a fourth year of OLE treatment. Dosing will remain consistent and there is no requirement for dose adjustment or further titration upon entry into years 2, 3, or 4.

Assessment visits have been added at Week 78, Week 104, Week 130, Week 156, and Week 182 (relative to Visit B1). Investigational medicinal product (IMP) dispensing visits have also been added between assessment visits in years 2, 3, and 4 to ensure resupply volumes are manageable for both patients and dispensing staff. Attendance of the patient is not required for the dispensing visits provided the primary caregiver is able to attend. However, it is preferred that the patient attend where possible.

Patients will complete the OLE phase when GWP42003-P is approved in TSC and is commercially available to the patient, or after a maximum of 4 years of OLE treatment, whichever occurs first. Following completion of the OLE, patients who do not immediately continue to use commercial GWP42003-P will commence a 10-day taper period (tapering 10% per day) before attending an End of Taper visit. A safety follow-up telephone call will be completed 2 weeks after the End of Taper visit and a safety Follow-up visit will be completed 4 weeks after the End of Taper visit.

3 TREATMENT SCHEMATIC DIAGRAM

- ^a End of Treatment/Withdrawal Visit will occur: 1) following early withdrawal from the trial; 2) in place of the next scheduled clinic visit (assessment or resupply) when GWP42003-P is approved in TSC and is commercially available to the patient; or 3) after a maximum of 4 years of OLE treatment (i.e., 208 weeks [± 7 days] from Visit B1); whichever occurs first.
- ^b Only required for patients who withdraw from the trial or complete treatment but do not immediately continue to use commercial GWP42003-P.
- ^c Safety Telephone Call must be made 2 weeks (+3 days) after the patient's last dose of IMP.
- ^d This must be made 4 weeks (+3 days) after the patient's last dose of IMP and can be conducted by telephone.
- ^e Visits B13, B14, B16, B17, B19, B20, B22, B23, B25, B26, B28, and B29 – Resupply visits (± 7 days).

4 DESIGN AND PROCEDURES

Patients and their parent(s)/legal representative will be invited to participate in years 2, 3, and 4 of the OLE when they reach Visit B10 of the OLE phase. They will be issued with additional OLE patient information and informed assent or the patient/parent(s)/legal representative information and informed consent (as applicable). Following adequate time to discuss the additional visits with the investigator, nurse, relatives or caregiver, patients/parent(s)/legal representatives who provide written informed consent/assent at Visit B10 will continue in the OLE.

Patients will continue to make weekly interactive voice response system (IVRS) diary calls throughout their second, third, and fourth years of OLE participation.

4.1 Visit B10 (Week 52)

In addition to the visit schedule outlined in Section 9.1.2.10 of the main protocol, patients treated in the US who provide written informed consent/assent (see [Section 5](#)) will receive sufficient open-label IMP for 9 weeks' home dosing and will be instructed to maintain consistent dosing. An additional dose calculator and paper diary will be issued, and patients will be trained on their appropriate use.

The Study Medication Use and Behavior Survey should not be administered at Visit B10 for patients entering the second year of the OLE. The investigator must record the patient's attendance at the visit and confirm their continued participation.

4.2 Resupply Visits B13 (Week 61), B14 (Week 70), B16 (Week 87), B17 (Week 96), B19 (Week 113), B20 (Week 122), B22 (Week 139), B23 (Week 148), B25 (Week 165), B26 (Week 174), B28 (Week 191), and B29 (Week 200)

Visits B13, B14, B16, B17, B19, B20, B22, B23, B25, B26, B28, and B29 will occur 61, 70, 87, 96, 113, 122, 139, 148, 165, 174, 191, and 200 weeks after Visit B1, respectively. A visit window of ± 7 days from the scheduled visit date is permitted, but it is preferred that the visit is performed on the scheduled visit day where possible.

Attendance of the patient is not required for resupply visits provided the primary caregiver is able to attend. However, it is preferred that the patient attend where possible.

Each visit will comprise a review of concomitant medications (including antiepileptic drugs [AEDs]), epilepsy-related hospitalizations and adverse events (AEs).

The investigator must assess adherence to the dosing regimen by reviewing the patient's diary and IVRS data, record the patient's/caregiver's attendance at the visit, and confirm the outcome of the visit.

All IMP (used and unused) will be collected and a check of the returned IMP against usage should be made. Patients/caregivers will then receive sufficient IMP until the next scheduled visit.

4.3 Assessment Visits B15 (Week 78), B18 (Week 104), B21 (Week 130), B24 (Week 156), and B27 (Week 182)

Visits B15, B18, B21, B24, and B27 will occur 78, 104, 130, 156, and 182 weeks after Visit B1, respectively. A visit window of ± 7 days from the scheduled visit date is permitted, but it is preferred that the visit is performed on the scheduled visit day where possible.

The following assessments will be made at each visit:

- Concomitant medications (including AEDs)
- Physical examination (including height and body weight)
- 12-lead electrocardiogram (ECG)
- Vital signs
- Epilepsy-related hospitalizations
- AEs
- Subject Global Impression of Change in Seizure Duration (SGIC-SD)/Caregiver Global Impression of Change in Seizure Duration (CGIC-SD)
- Suicidality, assessed in accordance with Section 9.2.12.8 of the main protocol

At each assessment visit, clinical laboratory samples (blood and urine [where possible]), including a pregnancy test if appropriate (using both a serum sample and a urine dipstick), will be taken for hematology, biochemistry, urinalysis, and determination of serum insulin-like growth factor-1 (IGF-1) levels (for patients less than 18 years of age) to be performed by the central laboratory. Provided that the risk/benefit outcome is favorable in the investigator's opinion, prior to the first daily dose of IMP, a blood sample will be taken for analysis of plasma concentrations of concomitant AEDs.

The investigator must assess adherence to the dosing regimen by reviewing the patient's diary and IVRS data, record the patient's attendance at the visit, and confirm the outcome of the visit.

All IMP (used and unused) will be collected and a check of the returned IMP against usage should be made. Patients/caregivers will then receive sufficient IMP until the next scheduled visit.

In addition to the above, the following assessments will be made at Visit B18 and Visit B24:

- Details of menstruation (for females)
- Tanner staging (patients aged 10–17 [inclusive] only)
- Quality of Life in Childhood Epilepsy (QOLCE)/Quality of Life in Epilepsy (QOLIE-31-P)
- Subject Global Impression of Change (SGIC)/Caregiver Global Impression of Change (CGIC)
- Physician Global Impression of Change (PGIC)
- Wechsler Tests
- Child Behavior Checklist (CBCL)/Adult Behavior Checklist (ABCL)
- Social Communication Questionnaire (SCQ)
- Vineland Adaptive Behavior Scales, Second Edition (Vineland-II)

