Section 9.1.2.7 Assessment Visit B6 (Day 183) p. 79 (Continued)	SD/CGIC-SD, Wechsler Tests, CBCL/ABCL, SCQ and the Vineland-II. Suicidality will be assessed using the C-SSRS/Children's C-SSRS (Since Last Visit) or, in patients with profound cognitive impairment, by interview and clinical judgment. The investigator must assess adherence to the dosing regimen by reviewing the patient's diary and IVRS data, record the patient's attendance at the visit and confirm the outcome of the visit. All IMP (used and unused) will be collected and a check of the returned IMP against usage should be made. Patients/caregivers will then receive a three-month supply of IMP.	QOLCE/QOLIE-31-P, PGIC, SGIC/CGIC, SGIC-SD/CGIC-SD, Wechsler Tests, CBCL/ABCL, SCQ and the Vineland-II. Suicidality will be assessed using the C-SSRS/Children's C-SSRS (Since Last Visit) or, in patients with profound cognitive impairment, by interview and clinical judgment. The investigator must assess adherence to the dosing regimen by reviewing the patient's diary and IVRS data, record the patient's attendance at the visit and confirm the outcome of the visit. All IMP (used and unused) will be collected and a check of the returned IMP against usage should be made. Patients/caregivers will then receive sufficient open label IMP for eight weeks' home dosing.	See Section 2.10
Section 9.1.2.8 Visit B7 (Day 232, Re-supply Visit) p. 80	Section 9.1.2.5.2 Re-supply Visits (...) Re-supply Visits will comprise a review of concomitant medications (including AEDs), epilepsy-related hospitalizations and AEs.	(...) Section 9.1.2.8 Visit B7 † (Day 232, Re-Supply Visit) (...) This visit will occur 231 days after Visit B1. A visit window of ±7 days† from the scheduled visit date is permitted, but it is preferred that the visit is	See Section 2.10 See Section 2.1

Revised Protocol Section Number, Heading and Page Number	Original Wording from Clinical Protocol Version 2 Date 21 OCT 2015 (Deleted wording is struck through and in bold)	Revised Wording from Clinical Protocol Amendment 2 (Clinical Protocol V3 25Aug16) (Revised wording is underscored and in bold)	Rationale for the amendment

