Visit B8 (Day 274) p. 80-81 (Continued)		
performed on the scheduled visit day where possible. The following observations will be made at Visit B8: concomitant medications, (including AEDs), physical examination (including height and body weight), ECG, vital signs, epilepsy-related hospitalizations and AEs. Clinical laboratory samples (blood and urine [where possible]), including a pregnancy test if appropriate (using both a serum sample and a urine dipstick), will be taken for hematology, biochemistry and urinalysis to be performed by the central laboratory. Provided that the risk/benefit outcome is favorable in the investigator’s opinion, prior to the first daily dose of IMP, a blood sample will be taken for analysis of plasma concentrations of concomitant AEDs. The following assessments will also be performed: SGIC-SD/CGIC-SD. Suicidality will be assessed using the C-SSRS/Children’s C-SSRS (Since Last Visit) or, in patients with profound cognitive impairment, by interview and clinical judgment. The investigator must assess adherence to the dosing
	

Revised Protocol Section Number, Heading and Page Number	Original Wording from Clinical Protocol Version 2 Date 21 OCT 2015 (Deleted wording is struck through and in bold)	Revised Wording from Clinical Protocol Amendment 2 (Clinical Protocol V3 25Aug16) (Revised wording is underscored and in bold)	Rationale for the amendment
Section 9.1.2.9 Visit B8 (Day 274) p. 80-81 (Continued)		regimen by reviewing the patient's diary and IVRS data, record the patient's attendance at the visit and confirm the outcome of the visit. All IMP (used and unused) will be collected and a check of the returned IMP against usage should be made. Patients/caregivers will then receive sufficient open label IMP for eight weeks' home dosing.	See Section 2.10

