Patient IVRS and paper diary review (seizures, AE information, concomitant AEDs, rescue medication, IMP dosing)	X	X		X	X		X	X		X	X		X	X		X	X		X	X		
IMP dispensing	X	X		X	X		X	X		X	X		X	X		X	X		X			
Collection of IMP	X	X		X	X		X	X		X	X		X	X		X	X		X	X		
IMP compliance review	X	X		X	X		X	X		X	X		X	X		X	X		X	X		
Study Medication Use and Behavior Survey																			X ^e			

- ^a End of Treatment/Withdrawal Visit will occur: 1) following early withdrawal from the trial; 2) in place of the next scheduled clinic visit (assessment or resupply) when GWP42003-P is approved in TSC and is commercially available to the patient; or 3) after a maximum of 4 years of OLE treatment (i.e., 208 weeks [± 7 days] from Visit B1); whichever occurs first.
- ^b Only required for patients who withdraw from the trial or complete treatment but do not immediately continue to use commercial GWP42003-P.
- ^c Safety Telephone Call must be made 2 weeks (+3 days) after the patient's last dose of IMP.
- ^d Follow-up Visit required for patients who withdraw from the trial or complete treatment but do not immediately continue to use commercial GWP42003-P. This must be made 4 weeks (+3 days) after the patient's last dose of IMP and can be conducted by telephone.
- ^e Performed at final dosing visit (End of Treatment/Withdrawal visit or End of Taper visit, as applicable) for patients 12 years of age and older only.

A double-blind, randomized, placebo-controlled study to investigate the efficacy and safety of cannabidiol (GWP42003-P, CBD) as add-on therapy in patients with tuberous sclerosis complex who experience inadequately-controlled seizures

Study Code: GWEP1521

EudraCT Number: 2015-002154-12

**CLINICAL PROTOCOL ANNEX 1 (US ONLY)
AMENDMENT NUMBER: 2**

**to be incorporated into the Protocol Annex, creating
CLINICAL PROTOCOL ANNEX 1 VERSION 3
(US ONLY),
DATE 15 APRIL 2019**

GW Research Ltd

[name]

United Kingdom

Tel: PPD

Fax: PPD

Confidentiality Statement

This document contains confidential information of GW Research Ltd (GW) that must not be disclosed to anyone other than the recipient study staff and members of the institutional review board or independent ethics committee. This information cannot be used for any purpose other than the evaluation or conduct of the clinical investigation without the prior written consent of GW.

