4.1 Visit B10 (Week 52)

In addition to the visit schedule outlined in Section 9.1.2.10 of the main protocol, patients treated in Poland who provide written informed consent/assent (see [Section 5](#)) will receive sufficient open-label IMP for 9 weeks' home dosing and will be instructed to maintain consistent dosing. An additional dose calculator and paper diary will be issued, and patients will be trained on their appropriate use.

The Study Medication Use and Behavior Survey should not be administered at Visit B10 for patients entering the second year of the OLE. The investigator must record the patient's attendance at the visit and confirm their continued participation.

4.2 Resupply Visits B13 (Week 61), B14 (Week 70), B16 (Week 87), B17 (Week 96), B19 (Week 113), B20 (Week 122), B22 (Week 139), and B23 (Week 148)

Visits B13, B14, B16, B17, B19, B20, B22, and B23 will occur 61, 70, 87, 96, 113, 122, 139, and 148 weeks after Visit B1, respectively. A visit window of ± 7 days from the scheduled visit date is permitted, but it is preferred that the visit is performed on the scheduled visit day where possible.

Attendance of the patient is not required for resupply visits provided the primary caregiver is able to attend. However, it is preferred that the patient attend where possible.

Each visit will comprise a review of concomitant medications (including antiepileptic drugs [AEDs]), epilepsy-related hospitalizations and adverse events (AEs).

The investigator must assess adherence to the dosing regimen by reviewing the patient's diary and IVRS data, record the patient's/caregiver's attendance at the visit, and confirm the outcome of the visit.

All IMP (used and unused) will be collected and a check of the returned IMP against usage should be made. Patients/caregivers will then receive sufficient IMP until the next scheduled visit.

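### In the US and Poland annexes, the nine-week supply at Visit B10 exactly equals the nominal interval to the next dispensing visit and leaves nothing for the permitted visit windows

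*Protocol*

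**What the plan says.** Section 4.1 of Annex 1 (US, V3) fixes the quantity given at Visit B10, Week 52: continuing patients "will receive sufficient open-label IMP for 9 weeks' home dosing and will be instructed to maintain consistent dosing". Section 4.1 of Annex 2 (Poland) sets the same quantity: "will receive sufficient open-label IMP for 9 weeks' home dosing".

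The next dispensing visit is B13, at Week 61 (Section 4.2 of both annexes). For that visit, "A visit window of ± 7 days from the scheduled visit date is permitted". The window row of the Schedule of Assessments in Appendix 1 of both annexes gives B10 a window of 7 days either side as well. The same schedules mark "Collection of IMP" at B10, so leftover year-1 stock is taken back there.

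B10 is the only one of the annexes' routine dispensing visits with a fixed number of weeks. From B13 onward the instruction is "Patients/caregivers will then receive sufficient IMP until the next scheduled visit". It applies to 17 visits in Annex 1 (12 resupply and 5 assessment) and 11 in Annex 2 (8 and 3).

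For comparison, the revised text in Protocol Amendment 2 for Visits B6 and B8 (Sections 9.1.2.7 and 9.1.2.9) has patients "receive sufficient open label IMP for eight weeks", where the following resupply visit is seven weeks away.

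**The concern.** The quantity is sized to the nominal interval, while the same annexes let both ends of that interval move by a week. A site can dispense what is written and see the patient on permitted dates, and the patient can still run out before B13.

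The patients are in the trial because their seizures are inadequately controlled. The annexes were written to keep access continuous, and the sentence that sets the supply also asks for steady dosing. A supply lapse would be an abrupt stop. The 10-day taper in Section 4.4 is for patients who complete or withdraw. Nothing in the annexes says what to do if supply runs out between visits, or how to restart afterwards.

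The documents give no figure for the seizure risk of such a gap, and none is claimed here.

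**Working it through.** **Inputs**

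- Supply at B10: 9 weeks = 9 × 7 = 63 days (Section 4.1, both annexes).
- B10: Week 52, i.e. 52 × 7 = 364 days after B1, window ±7 days (Appendix 1, both annexes; the Amendment 2 text for Section 9.1.2.11 agrees).
- B13: Week 61, i.e. 61 × 7 = 427 days after B1, window ±7 days (Section 4.2, both annexes).
- Carry-over stock: none provided for, because held IMP is collected at B10.

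**The plan's own figure.** 427 − 364 = 63 days, equal to the supply. The nine weeks is correct for the nominal dates, and the reserve is 63 − 63 = 0.

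**With the windows.** Let w10 and w13 be the shifts of the two visits in days, each between −7 and +7:

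Gap = max(0, (427 + w13) − (364 + w10) − 63) = max(0, w13 − w10)

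| B10 | B13 | Interval (days) | Days without IMP |
|---|---|---|---|
| on time | on time | 63 | 0 |
| on time | 7 days late | 70 | 7 |
| 7 days early | on time | 70 | 7 |
| 7 days early | 7 days late | 77 | 14 |
| 7 days early | 7 days early | 63 | 0 |
| 7 days late | 7 days late | 63 | 0 |
| 7 days late | on time | 56 | 0 (7 spare) |
| on time | 7 days early | 56 | 0 (7 spare) |
| 7 days late | 7 days early | 49 | 0 (14 spare) |

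A gap arises whenever B13 falls later, relative to its schedule, than B10 did.

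**Year-1 comparator.** B6 to B7 is 232 − 183 = 49 days and B8 to B9 is 323 − 274 = 49 days. Eight weeks is 56 days, so the reserve is 56 − 49 = 7 days. One visit a week off schedule gives a 56-day interval and no shortfall. Visits at opposite extremes (for example Day 176 to Day 239) give 63 days and a shortfall of 63 − 56 = 7. Year 1 therefore absorbed one off-schedule visit, but not two in opposite directions. B10 absorbs none.

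**Check of the remedy.** Supplying to the last day of the B13 window means 62 × 7 = 434 days after B1:

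Supply = 434 − (364 + w10) = 70 − w10

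This is 70 days if B10 is on time, 77 if it is 7 days early and 63 if it is 7 days late. The gap becomes max(0, w13 − 7), which is 0 throughout the window. A flat 10 weeks (70 days) would still leave up to 77 − 70 = 7 days uncovered at the extreme. A flat 11 weeks (77 days) would cover every combination.

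**The case against.** The strongest reply is that nothing is misstated. Nine weeks matches a nine-week interval, the wording says what the supply must suffice for and sets no ceiling, and a site may give more. That is true, but a site that gives exactly what is written has complied, and the shortfall follows. Whole-bottle rounding may leave some surplus; the text does not promise it.

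Second, the main body of the protocol is not among the pages at hand, and a general overage rule there cannot be excluded. This stands as a limit: the finding is that no reserve is stated in the text available.

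Third, the wording used from B13 onward states no reserve either, so B10 is not unique. That is fair, and the later wording is not offered as a model. It does at least let a site size the supply to the appointment actually booked, which a fixed count does not.

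Fourth, the comparator comes from Amendment 2 and itself falls 7 days short at the extreme. It shows that slack was allowed in year 1. It does not show a rule that supply must cover the windows.

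Fifth, 14 days needs both visits at opposite limits. The annexes prefer the scheduled day, and a caregiver may collect alone at B13. This makes a gap less likely without ruling it out, and the 7-day case needs only one visit a week off.

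Last, the annexes want resupply volumes kept manageable. To illustrate with an assumed 60 kg patient at the 50 mg/kg/day maximum and 100 mg/mL: 60 × 50 / 100 = 30 mL/day, so 14 extra days is 420 mL on top of 63 × 30 = 1,890 mL. That is a real but one-off burden, and it arises only when B10 is a full week early.

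**Conclusion.** The concern holds, as a minor point of dosing continuity and safety. Visits that respect every window can leave a patient without IMP for up to 7 days when one visit is a week off schedule, and up to 14 days at the extreme. There is no gap when B13 is no later against its schedule than B10 was.

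This assumes that a site dispenses 63 days and no more, that stock held at B10 is collected as scheduled, and that no overage rule in the unseen main protocol applies. The gap is possible rather than expected, and how often it would occur cannot be estimated from the documents. It affects only patients in the US and Poland who continue past Week 52. The blinded phase and the primary analysis are untouched.

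**What to change.** In Section 4.1 of both annexes, replace the nine-week quantity with IMP sufficient to the last day of the B13 visit window, Week 62 from Visit B1. Preferably also add one sentence to Sections 4.2 and 4.3 of both annexes saying that supply until the next scheduled visit includes that visit's window.

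The cost is one wording change per annex, the optional clarifying sentence, and a matching change in the IVRS if the quantity is set there. At most two extra weeks of IMP go out at B10. Unused IMP is collected at B13, so stock does not accumulate.
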